## Document History

Document	Version Date
Amendment 1	10 May 2022
Original protocol	25 Jun 2021

This amendment incorporates all revisions to date, including amendments made at the request of country health authorities and IRBs/ECs and any global protocol administrative clarification letter.

## Protocol Amendment Summary of Changes Table

### Amendment 1 (10 May 2022)

Section # and Name	Description of Change	Brief Rationale	Substantial or Nonsubstantial
Section 1.1. Synopsis, Subsection “Number of Participants”; Section 4.1. Overall Design, Subsection “Number of Participants”; Section 4.2. Scientific Rationale for Study Design	
The following statement was updated:
 
Original statement:            If more than 2 participants discontinue or withdraw before completing at least the follow-up visit at Day 100, participants may be replaced at the discretion of the investigator upon alignment with the sponsor.
 
Updated statement:            If more than 2 participants discontinue or withdraw before completing at least the follow-up visit at Day 100, or if there are participants whose PK samples are considered to be non-evaluable with respect to the primary PK objective, additional
	
To allow additional participants to enroll in the study in the event of participants whose PK samples are considered to be non-evaluable with respect to the primary PK objective or if more than 2 participants discontinue or withdraw before completing at least the follow-up visit at Day 100, to ensure approximate 10 participants could provide evaluable PK samples for no less than Day 100 follow-up visit.
	Substantial

Section # and Name	Description of Change	Brief Rationale	Substantial or Nonsubstantial
	
participants may be enrolled upon alignment between the sponsor and the investigator such that approximate 10 participants could provide evaluable PK samples for no less than Day 100 follow-up visit. For participants whose PK samples are considered to be non-evaluable with respect to the primary PK objective, their PK sample collection will stop for ethic consideration.
		

Section 9.5. Sample Size Determination
	
The following statement was added:
 
If more than 2 participants discontinue or withdraw before completing at least the follow-up visit at Day 100, or if there are participants whose PK samples are considered to be non-evaluable with respect to the primary PK objective, additional participants may be enrolled upon alignment between the sponsor and the investigator such that approximate 10 participants could provide evaluable PK samples for no less than Day 100 follow-up visit.
	
To allow additional participants to enroll in the study in the event of participants whose PK samples are considered to be non-evaluable with respect to the primary PK objective or if more than 2 participants discontinue or withdraw before completing at least the follow-up visit at Day 100, to ensure approximate 10 participants could provide evaluable PK samples for no less than Day 100 follow-up visit.
	
Substantial

Section # and Name	Description of Change	Brief Rationale	Substantial or Nonsubstantial
Section 1.3. Schedule of Activities	ECG was updated to be measured on Day -1 instead of Day 1.	To keep consistent with Exclusion Criteria #18 evaluation (Day -1/baseline) and to align with site practice.	Nonsubstantial
Section 1.3. Schedule of Activities	In the footnote “h”, the statement of “at least 48 hours before and” was removed for COVID-19 questionnaire.	To align with site practice.	Nonsubstantial
Section 5.2. Exclusion Criteria #2	The word “syphilis” was added to statement, the updated statement being: History of HIV infection, hepatitis B, or hepatitis C; positive testing for HIV, syphilis , HBsAg, or HCVAb.	To keep consistent with assessment requirement listed in Section 1.3 Schedule of Activities.	Nonsubstantial
Section 5.2. Exclusion Criteria #17	Update “≤50 bpm” to “<50 bpm”.	To correct a typo.	Nonsubstantial
Section 8.2.4. Electrocardiogram	The original statement of “Appendix 7” was updated to “Appendix 6”:  ECG values of potential clinical concern are listed in Appendix 6 .	To correct a typo.	Nonsubstantial
Section 8.2.5. Clinical Safety Laboratory Assessments	The original statement of “Appendix 6” was updated to “Appendix 5”:  See Appendix 5 for suggested actions and follow-up assessments in the event of potential drug-induced liver injury.	To correct a typo.	Nonsubstantial

Section # and Name	Description of Change	Brief Rationale	Substantial or Nonsubstantial
Section 9.4. Interim Analyses	
In the second sentence of the paragraph, the word “However” was deleted and “agency communication” was added, the updated sentence being:
 
As this is an sponsor-open study, the sponsor may conduct unblinded reviews of the data during the course of the study for the purpose of safety assessment, facilitating PK/PD modeling, agency communication, and/or supporting clinical development.
	
The word “However” was deleted to align with mandatory template text.
 
The wording “agency communication” was added to reflect updated purpose of potential unblinded data review.
	Nonsubstantial
Section 10.2. Appendix 2: Clinical Laboratory Tests	Syphilis test was added to “Other” safety laboratory assessment.	To keep consistent with assessment requirement listed in Section 1.3 Schedule of Activities.	Nonsubstantial
Section 10.4.4. Contraception Methods	The word “Injectable” was removed from “6. Combined [estrogen- and progestogen-containing] hormonal contraception associated with inhibition of ovulation”.	To align with protocol template updates.	Nonsubstantial

## 1. PROTOCOL SUMMARY

### 1.1. Synopsis

**Brief Title:** A Phase 1 Study to Evaluate the Pharmacokinetics, Safety, and Tolerability Following a Single Dose of PF-06823859 in Healthy Chinese Participants

#### Rationale

The purpose of this study is to evaluate the single-dose PK, safety, and tolerability of PF-06823859 after single IV administration to healthy adult Chinese participants. The information of PK, safety, and tolerability in healthy Chinese participants is being collected to support future PF-06823859 clinical development as well as drug registration in China.

#### Objectives and Endpoints

Objectives	Endpoints
Primary:	Primary:

To evaluate the PK profile of single IV dose of 900 mg PF-06823859 in healthy Chinese participants.

To determine the safety and tolerability of single IV dose of 900 mg PF-06823859 in healthy Chinese participants.

	

Serum PF-06823859 primary PK parameters, as permitted by data: <math>C_{max}</math>, <math>T_{max}</math>, <math>AUC_{14day}</math>, <math>AUC_{28day}</math>, <math>AUC_{inf}</math>, and <math>t_{1/2}</math>.

Assessments of AEs/SAEs including infusion site reactions and viral infections, vital signs, ECGs and laboratory tests.

Secondary:	Secondary:

To further evaluate the PK of PF-06823859

To evaluate the immunogenicity of PF-06823859.

	

Serum PF-06823859 PK parameters, as permitted by data: <math>C_{max}</math> (dn), <math>AUC_{last}</math>, <math>AUC_{last}</math> (dn), <math>AUC_{inf}</math> (dn), CL, <math>V_z</math>, and MRT.

Incidence of the development of ADA and Nab.

#### Overall Design

This is a Phase 1, randomized, double-blind, sponsor-open, placebo-controlled study to evaluate the PK, safety, and tolerability following a single dose of PF-06823859 (900 mg) in healthy Chinese participants.

#### Number of Participants

Approximately 12 participants will be enrolled into the study. Approximately 10 participants will be randomized to PF-06823859 and approximately 2 participants will be randomized to placebo.

If more than 2 participants discontinue or withdraw before completing at least the follow-up visit at Day 100, or if there are participants whose PK samples are considered to be non-evaluable with respect to the primary PK objective, additional participants may be enrolled upon alignment between the sponsor and the investigator such that approximate 10 participants could provide evaluable PK samples for no less than Day 100 follow-up visit. For participants whose PK samples are considered to be non-evaluable with respect to the primary PK objective, their PK sample collection will stop for ethic consideration.

### **Intervention Groups and Duration**

Within 28 days of successful completion of the screening process, eligible participants will be enrolled and randomized to receive a single IV infusion of PF-06823859 or placebo. Participants will be admitted into the CRU approximately 1 day prior to dosing and are required to remain in the CRU through completion of Day 5 evaluations. Participants will return to the CRU for outpatient follow-up visits through Day 157.

**Data Monitoring Committee or Other Independent Oversight Committee: No**

### **Statistical Methods**

Statistical objective is exploratory. Only descriptive analyses will be performed.

#### **1.2. Schema**

Not applicable.

### 1.3. Schedule of Activities

The SoA table provides an overview of the protocol visits and procedures. Refer to the [STUDY ASSESSMENTS AND PROCEDURES](#) section of the protocol for detailed information on each procedure and assessment required for compliance with the protocol.

The investigator may schedule visits (unplanned visits) in addition to those listed in the SoA table, in order to conduct evaluations or assessments required to protect the well-being of the participant.

Visit Identifier a Abbreviations used in this table may be found in Appendix 7 .	Screening	CRU Confinement										Follow-Up							ET			
		-28 to -2	-1	1					2	3	4	5	8	15	29	43	57	71		100	127	157
Days Relative to Day 1	-	-	-					-	-	-	-	±1	±1	±1	±3	±3	±3	±3	±3	±3	±3	-
Visit Window (days)	-	-	-					-	-	-	-	±1	±1	±1	±3	±3	±3	±3	±3	±3	±3	-
Hours After Dose			0 b	1	2	6	12	24	48	72	96	-	-	-	-	-	-	-	-	-	-	
Informed consent	X																					
Demography	X																					
CRU confinement		X	→	→	→	→	→	→	→	→	X											
Visit to the CRU	X	X									X	X	X	X	X	X	X	X	X	X	X	
Inclusion/exclusion criteria	X	X																				
Medical/medication history (update)	X	X																				
History of illicit drug, alcohol and tobacco use	X	X																				
Report prior or concomitant treatments	X	X	→	→	→	→	→	→	→	→	X	X	X	X	X	X	X	X	X	X	X	
Contraception check	X	X									X	X	X	X	X	X	X	X	X	X	X	
Physical exam (including height and weight at screening, only) c	X	X																			X	
Single 12-Lead ECG	X	X								X			X		X		X	X	X	X	X	
Supine blood pressure, pulse rate and temperature	X		X							X			X		X		X	X	X	X	X	
Chest radiograph d	X																				X	
Serious and nonserious AE monitoring	X	→	→	→	→	→	→	→	→	→	X	X	X	X	X	X	X	X	X	X	X	
Study intervention administration			X e																			
Safety laboratory (after ≥4-hour fast) including PT, INR, aPTT	X	X						X			X	X	X		X		X	X	X	X	X	
Viral surveillance (CMV, VZV, EBV, HHV6, HSV-1, HSV-2)	X										X		X		X					X	X	

Visit Identifier a Abbreviations used in this table may be found in Appendix 7 .	Screening	CRU Confinement										Follow-Up							ET		
		-28 to -2	-1	1					2	3	4	5	8	15	29	43	57	71		100	127
Days Relative to Day 1	-28 to -2	-1	1					2	3	4	5	8	15	29	43	57	71	100	127	157	-
Visit Window (days)	-	-	-					-	-	-	-	±1	±1	±1	±3	±3	±3	±3	±3	±3	-
Hours After Dose		0 b	1	2	6	12	24	48	72	96	-	-	-	-	-	-	-	-	-	-	
FSH in females amenorrheic ≥12 months, only	X																				
Pregnancy test (WOCBP only)	X	X									X		X		X	X	X	X	X	X	
HIV, HBsAg, HBsAb, HBcAb, HCVAb, syphilis	X																				
HBV DNA, if applicable f	X														X				X	X	
Interferon Gamma Release Assay g	X																				
COVID-19 questionnaire h	X	X									X	X	X	X	X	X	X	X	X	X	
COVID-19 testing i	X								X												
COVID-19 check temperature j	X	X	X				X	X	X	X	X	X	X	X	X	X	X	X	X	X	
Pharmacokinetic blood sampling		X	X k	X	X	X	X	X		X		X	X	X	X	X	X	X	X	X	
Immunogenicity (ADA, NAb) l		X									X	X		X	X	X	X	X	X		
Urine drug testing	X	X																			
Urinalysis (after ≥4-hour fast)	X	X					X			X	X	X	X	X		X	X	X	X		

- a. Day relative to start of study intervention (Day 1).
- b. Pre-dose (except for study intervention administration).
- c. A full physical examination may be done at screening or Day -1. Brief physical examination to follow-up open AEs after Day -1 may be done.
- d. Chest X-ray or other appropriate diagnostic image (ie, CT or MRI) results within 12 weeks of the screening visit, otherwise a chest X-ray must be performed and results obtained prior to dosing in the study. See [Section 8.2.2](#).
- e. Participants should be continuously monitored for infusion related reactions from start of study intervention administration until the end of infusion.
- f. Participants who are HBsAg negative but HBcAb negative and HBsAb positive without unequivocal documentation of prior HBV vaccination or who are HBsAg negative but HBcAb positive and HBsAb positive are required to undergo HBV DNA reflex testing at screening. If HBV DNA is undetectable in the HBV DNA reflex testing in screening and the participant is enrolled in the study, HBV DNA testing must be performed on. If HBV DNA is undetectable in the HBV DNA reflex testing in screening and the participant is enrolled in the study, HBV DNA testing must be performed on Day 71, 157 and ET. See [Section 8.2.5.1](#).
- g. Acceptable IGRA assays are QuantiFERON®-TB Gold In-Tube (QFT-GIT) test and T-SPOT®-TB test. A documented TB test performed within 12 weeks prior to Day 1 is acceptable. Participants with a history of tuberculosis may not require TB testing as per the protocol exclusion criteria in [Section 5.2](#).
- h. Check exposure to positive participant, residence or travel in area of high incidence and COVID-19 related signs and symptoms. To be done at each visit.
- i. The testing for COVID-19 pathogen by PCR will be performed within 72 hours prior to admission on Day -1. In addition, a subsequent COVID-19 test will be performed after 4 days (ie, upon completion of 4 × 24 hours in house), or if they develop COVID-19 like symptom.
- j. To be done at least daily during residence and at every follow-up visit after discharge from the CRU.
- k. End of infusion (ie, 1-hour post-dose).

Visit Identifier a Abbreviations used in this table may be found in Appendix 7 .	Screening	CRU Confinement											Follow-Up							ET
		-28 to -2	-1	1				2	3	4	5	8	15	29	43	57	71	100	127	
Days Relative to Day 1	-28 to -2	-1	1				2	3	4	5	8	15	29	43	57	71	100	127	157	-
Visit Window (days)	-	-	-				-	-	-	-	±1	±1	±1	±3	±3	±3	±3	±3	±3	-
Hours After Dose			0 b	1	2	6	12	24	48	72	96	-	-	-	-	-	-	-	-	-

l. Participants with positive results may be requested to return for additional follow-up for up to approximately 3 months after final visit.

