#### Number of Participants

Approximately 12 participants will be enrolled into the study. Approximately 10 participants will be randomized to PF-06823859 and approximately 2 participants will be randomized to placebo.

If more than 2 participants discontinue or withdraw before completing at least the follow-up visit at Day 100, or if there are participants whose PK samples are considered to be non-evaluable with respect to the primary PK objective, additional participants may be enrolled upon alignment between the sponsor and the investigator such that approximate 10 participants could provide evaluable PK samples for no less than Day 100 follow-up visit. For participants whose PK samples are considered to be non-evaluable with respect to the primary PK objective, their PK sample collection will stop for ethic consideration.

Within 28 days of successful completion of the screening process, eligible participants will be enrolled and randomized to receive a single IV infusion of PF-06823859 or placebo. Participants will be admitted into the CRU approximately 1 day prior to dosing and are required to remain in the CRU through completion of Day 5 evaluations. Participants will return to the CRU for outpatient follow-up visits through Day 157.

ADA levels will be monitored from samples collected at the times specified in the [SoA](#). Samples found to be positive will be further evaluated for NAb. Participants with positive results may be requested to return for additional follow-up for up to approximately 3 months after the last scheduled follow-up visit.

No formal interim analysis will be conducted for this study. As this is a sponsor-open study, the sponsor will conduct unblinded reviews of the safety, PK, and immunogenicity data through Day 28 after treatment administration to preliminarily assess any ethnic differences between Chinese and non-Chinese to support China joining future global PF-06823859 clinical development.

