#### **4.2. Scientific Rationale for Study Design**

This study is designed to characterize the PK, safety, and tolerability of PF-06823859 after single IV dose administration in healthy Chinese participants.

To date, no PK or safety data of PF-06823859 in Chinese are available. Although there is no expected relevant PK difference between Chinese and non-Chinese because monoclonal antibodies are generally known for the absence of ethnic differences in their distribution and elimination, similar to that of endogenous IgG, it is still important to characterize PK and establish safety in Chinese participants to support future PF-06823859 clinical development as well as drug registration in China. Information collected from this study allows comparison of PK and safety profiles of PF-06823859 in Chinese and non-Chinese participants.

Single-dose rather than repeated dosing is planned in the study due to the long PF-06823859 terminal half-life as well as the steady-state PK can be well predicted from single dose data based on information of Study C0251001. The study duration and frequency of each assessment were decided based on information of Study C0251001.

In order to sufficiently evaluate PK, safety, and tolerability of PF-06823859 in Chinese participants while at the same time considering the clinical practice and minimal necessity for PK evaluation, if more than 2 participants discontinue or withdraw before completing at least the follow-up visit at Day 100, or if there are participants whose PK samples are considered to be non-evaluable with respect to the primary PK objective, additional participants may be enrolled upon alignment between the sponsor and the investigator such that approximate 10 participants could provide evaluable PK samples for no less than Day 100 follow-up visit. For participants whose PK samples are considered to be non-evaluable with respect to the primary PK objective, their PK sample collection will stop for ethic consideration.

Assessment of clinical safety laboratory tests ([Appendix 2](#)), vital signs, 12-lead ECG, physical examinations, and AE monitoring will provide essential data to evaluate the safety and tolerability of PF-06823859. There is a potential risk of increased susceptibility to viral infections with IFN- $\beta$  blockade as with any antagonist of Type 1 interferon signaling (eg,

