3. ENDPOINTS AND BASELINE VARIABLES: DEFINITIONS AND CONVENTIONS

3.1. Primary Endpoint(s)

- Serum PF-06823859 primary PK parameters, as permitted by data: C_{max} , T_{max} , AUC_{14day} , AUC_{28day} , AUC_{inf} , and $t_{1/2}$,
- Assessments of AEs/SAEs including infusion site reactions and viral infections, vital signs, ECGs and laboratory tests.

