3.4. Baseline Variables

The baseline value for laboratory, 12-Lead ECG and vital signs is defined as the latest measurement prior to taking dose.

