6.5.3. Vital Signs

Vital signs will be summarized using Pfizer's implementation of CDISC standards. For each planned timepoint, absolute values and change from baseline values will be summarized with descriptive statistics.

Maximum absolute values and maximum change from baseline for vital signs will also be summarized descriptively by treatment using categories. Numbers and percentages of participants meeting the categorical criteria will be provided by treatment and individual values listed.

Categories for Vital Signs

Systolic BP (mm Hg)	min. <90	
Systolic BP (mm Hg) change from baseline	max. decrease ≥ 30	max. increase ≥ 30
Diastolic BP (mm Hg)	min. <50	
Diastolic BP (mm Hg) change from baseline	max. decrease ≥ 20	max. increase ≥ 20

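### No post-dose blood pressure or pulse is planned until 72 h after the start of the single 60-minute infusion, so the vital-sign tables have no planned early post-dose value

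*Protocol*

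**What the plan says.** The Schedule of Activities (Protocol 1.3) marks the row "Supine blood pressure, pulse rate and temperature" at screening, 0 h on Day 1, 72 h (Day 4), Days 15, 43, 71, 100, 127 and 157, and early termination. Footnote b makes the 0 h mark pre-dose. Protocol 6.1.1 sets a 60-minute infusion with time 0 at its start. Protocol 8.2 points to this schedule for the planned times of all safety assessments.

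The primary safety endpoint in SAP 3.1 is "Assessments of AEs/SAEs including infusion site reactions and viral infections, vital signs, ECGs and laboratory tests". Protocol 4.2 says that laboratory tests, "vital signs, 12-lead ECG, physical examinations, and AE monitoring will provide essential data to evaluate the safety and tolerability of PF-06823859".

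SAP 6.5.3 plans two summaries. The first is by time: "For each planned timepoint, absolute values and change from baseline values will be summarized with descriptive statistics". The second is by extremes: "Maximum absolute values and maximum change from baseline for vital signs will also be summarized descriptively by treatment using categories". The printed categories cover systolic BP below 90, diastolic BP below 50, systolic changes of 30 mm Hg or more and diastolic changes of 20 mm Hg or more. Baseline is "defined as the latest measurement prior to taking dose", which is the 0 h reading.

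On the choice of schedule, Protocol 4.2 says: "The study duration and frequency of each assessment were decided based on information of Study C0251001".

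**The concern.** The drug is given once, by infusion, and the protocol itself expects that infusion reactions may occur: Section 6.1.1.1 has rules for stopping and restarting. No BP or pulse is planned at any of those moments, or in the two days after.

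An asymptomatic fall or rise in BP, or a change in pulse, in that period would enter no table unless someone chose to measure it. Protocol 10.3.1 lets the investigator call a vital-sign change an adverse event when it is clinically significant, but that judgement needs a measurement. A reader of the study report would see counts for maximum decrease and maximum increase with no sign that the first 71 h after infusion had no planned observation.

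The early sponsor review is affected in the same way. Protocol 4.1 says "the sponsor will conduct unblinded reviews of the safety, PK, and immunogenicity data through Day 28 after treatment administration", in order to look for differences between Chinese and non-Chinese participants. That review would hold two planned post-dose BP and pulse readings per participant, neither from infusion day.

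**Working it through.** No sample-size or power figure is involved, so the check is a count of schedule columns.

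1. **Columns.** The header gives 21: screening, Day -1, then 0, 1, 2, 6, 12, 24, 48, 72 and 96 h, then Days 8, 15, 29, 43, 57, 71, 100, 127 and 157, then early termination.

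2. **Alignment.** The hours, CRU-visit, ECG, vital-sign and safety-laboratory rows each fill 21 columns. Dosing falls on 0 h, confinement runs from Day -1 to 96 h (Day 5), and the ECG row is marked on Day -1, as Amendment 1 requires.

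3. **Marks in the rows that matter.**

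| Row | Before dosing | 1 to 48 h | Next marks |
|---|---|---|---|
| BP, pulse, temperature | Screening, 0 h | none | 72 h, Days 15, 43, 71, 100, 127, 157 |
| ECG (gives heart rate) | Screening, Day -1 | none | 72 h, then the same days |
| PK blood draw | 0 h | 1, 2, 6, 12, 24, 48 h | 96 h onward |

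The PK row is on the second page of the schedule, where the extracted text is shifted; footnote k fixes its 1 h draw at the end of infusion.

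4. **Gap.** First post-dose reading minus end of infusion: 72 − 1 = 71 h. If an interrupted infusion runs to the 3-hour limit of Protocol 6.1.1.1: 72 − 3 = 69 h.

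5. **Sensitivity to misreading the table.** A slip of one column would put the first reading at 48 h or 96 h, a gap of 47 h or 95 h. Infusion day would still have no post-dose reading.

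6. **Planned post-dose readings.** 7 per participant, excluding early termination; 7 × 10 = 70 in the active arm. Number within 71 h of the end of a 60-minute infusion: 0. Available to the Day 28 review: 72 h and Day 15, so 2 per participant and 2 × 10 = 20 in the active arm.

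7. **After the fix.** Four added readings per participant (end of infusion, 2, 6 and 24 h): 4 × 10 = 40 active and 4 × 2 = 8 placebo, 48 in all. Then 4 of 7 + 4 = 11 planned post-dose readings (36%) fall in the first 24 h.

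**The case against.** The strongest reply is that participants are closely watched. Footnote e requires continuous monitoring for reactions during the infusion. Section 2.3 commits to intensive inpatient monitoring, and Section 6.1.1.1 acts on symptoms such as lightheadedness. Adverse event monitoring is continuous, temperature is checked at least daily, safety laboratory tests are taken at 24 h, and Section 8.2.3 permits extra BP and pulse readings when needed. All of this stands, and it narrows the gap to asymptomatic changes that nobody measures. But none of these provisions sets a BP or pulse time. A reader might infer that early safety capture is missing; the documents do not support that.

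A second reply is that assessment frequency rests on Study C0251001, whose data are not shown. That may be a good reason. The statement is general, however, and does not explain why BP and pulse are absent while six PK draws are made.

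Three other stronger readings also fail:
- Infusion day does have a planned reading: the pre-dose baseline. Only post-dose readings are absent.
- The SAP does not exclude unscheduled readings from the extremes. Only the first summary in 6.5.3 is tied to planned timepoints; the paragraph on maxima has no such limit and asks for individual values to be listed. The sponsor's data standards, which may settle the matter, are not visible.
- The comparison of Chinese with non-Chinese participants cannot be said to be compromised. The vital-sign schedule of C0251001 is not given, so comparable early readings may not exist.

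It is also fair to say that the study is descriptive, has about two placebo participants, and tests no hypothesis.

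**Conclusion.** The point holds as a limited gap in a named component of the primary safety endpoint. Of 70 planned post-dose BP and pulse readings in the active arm, none falls before 72 h. The by-timepoint tables therefore have no planned post-dose value for Days 1 to 3, and the extreme-value categories depend on unscheduled readings for that period. PK and adverse event capture are unaffected.

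This rests on the schedule as extracted from the PDF, on about 10 active participants, and on the protocol being followed as written. No rate of infusion-day BP or pulse change is assumed, so nothing is claimed about how often a change would be missed. The change is worth making because it is cheap and improves the description of tolerability, not because any stated conclusion would be wrong without it.

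**What to change.** 1. **Schedule of Activities.** Add supine BP and pulse at the actual end of infusion, at a few existing PK times (for example 2, 6 and 24 h), and at any infusion stop or restart. Take each before the PK draw, as Section 8.2.3 already asks.

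2. **Arm.** Section 8.2.3 asks for the same arm throughout and bars BP from the infusion arm. Take the pre-dose baseline and the added readings on the same non-infusion arm.

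3. **Protocol Section 8, only where a sampling catheter is used.** PK sampling is in the arm opposite the infusion (6.1.1), and Section 8 asks for vital signs before catheter insertion. With a catheter in place, these rules leave no arm for an end-of-infusion BP, so exempt the added readings from the catheter rule. With venipuncture there is no conflict.

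4. **SAP 6.5.3, optional.** State that minima and maximum changes use all post-dose readings, including unscheduled ones.

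If the sponsor keeps the present schedule because of C0251001, say so for vital signs and footnote the tables that the first planned post-dose BP and pulse are at 72 h.

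**Cost.** About 48 extra cuff readings for 12 participants, within existing confinement and at existing blood-draw times, plus any at a stop or restart. Section 8.2.3 permits added times, and Sections 8.4 and 8.7 say that added time points for planned assessments, once documented and approved, are not an amendment. The catheter exemption is a change to protocol text, and Section 10.1.1 requires IRB/EC approval of amendments before they are implemented.
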